### ACT Protocols

#### High Frequency Chest Wall Oscillating Vest (HFCWO-Vest)

All subjects will use the The Vest® System, Model 105 (Hill-Rom, Batesville, IN). Subjects will have the adjustable vest fitted during their screening visit. The following adaption of a previously-studied protocol will be used for device settings. Each treatment segment will be 4 minutes.

Segment:	1	2	3	4	5	6
Frequency, Hz:	8	9	10	18	19	20
Device Pressure	10*	10*	10*	6	6	6

\*or highest tolerated pressure setting

#### *Oscillating Positive Expiratory Pressure Device (OPEP Device)*

Subjects will be given an Aerobika® (Monaghan Medical Corporation, Plattsburgh, NY) oscillating positive expiratory pressure system on a resistance setting of 5, the maximum resistance setting on the device. Subjects will perform 10 exhalations from near TLC to near RV through the OPEP device at a respiratory rate no faster than 10 breaths / minute to avoid acute respiratory alkalosis. The resistance setting will be decreased as necessary so subjects can comfortably perform this breathing maneuver. Subjects will perform 10 exhalations through the device during each of the six ACT segments minutes followed by one huff-cough maneuver. A member of the research team will coach subjects on proper breathing and device technique.

#### *Vibration platform for Whole Body Vibration (WBV)*

WBV will be performed for 90 seconds during each ACT segment using the PowerPlate® (Performance Health Systems, Northbrook, IL) vibration platform. Subjects will be positioned seated on the powerplate, which will rest on a custom-made wooden box 12" high, so that height of the platform is approximately that of a standard chair. Holes in the top of box engage the rubber "feet" of the PowerPlate to keep it in place. Subjects are seated with their feet on the floor and hands in their laps, sitting up as straight as possible. The "high" amplitude will be used on the device. After each segment, subjects will perform a huff-cough maneuver and return to be seated in front of the gamma camera.

### ***Outcome Measures***

#### *Mucociliary Clearance*

Background and transmission scans will be performed per the MCC Standard Operating Procedure (see attachment) to subtract background radiation levels and allow identification of lung boundaries and regions of interest. The Tc-99 sulphur colloid radiotracer will be inhaled using our slow inhalation, large particle method. The subject will be positioned in front of the gamma camera, and images will be obtained for 16 minutes prior to any intervention. Sixteen minutes after particle inhalation, there will be a 40-minute intervention period with whichever ACT the subject is to receive during that study visit. Following the ACT period, there will be an additional 38 minutes of image capture. After an 86-minute break (i.e. 180 minutes after tracer inhalation), an identical MCC image capture period with ACT intervention will occur (Figure 3).

#### *Airway Signalling Molecule Assays*

#### *Exhaled Breath Condensate (EBC)*

EBC collections will be performed using the R-tube system. The subject will perform normal, tidal volume breathing through the chilled tube for 7 minutes, while wearing nose clips. The baseline collection will be performed at each study visit before inhaling isotope, and will be repeated immediately after the first ACT intervention at minute 56 (see Figure 3). EBC samples will be processing by adding an internal standard with isotopically labeled urea, purines, and

amino acids as previously described. Following this step, the EBC sample (plus internal standard) will be lyophilized and reconstituted to achieve a 20-fold increase in concentration before analysis by mass spectrometry.

EBC concentrations of purine metabolites (AMP, adenosine, hypoxanthine) will be measured using MS methods as previously described. In addition, we will utilize a recently installed AB Sciex 6500 triple quadrupole mass spectrometer available in our core center that has ~100-fold increased sensitivity relative to the Quantum Ultra mass spectrometer utilized in previous studies and should be ideal for assessing the low biomarker concentrations expected in EBC.

#### Fraction of Exhaled Nitric Oxide (FeNO)

FeNO will be measured using NIOX MINO® device by Aerocrine according to device instructions. FeNO measurement will be performed immediately before each EBC collection (i.e., before inhaling isotope and at minute 56).

#### *Sputum Collection and coughs*

All expectorated sputum from the start of the first ACT period through 274 minutes post isotope inhalation will be collected and weighed to assess total volume. Subjects will not be encouraged to cough outside of huff-cough maneuvers- rather, to cough only when naturally compelled to do so. Subjects will be encouraged to expectorate rather than swallow their sputum. This sputum will be analysed by total weight and percent solids. While MCC images are being obtained, subjects will be asked to minimize additional coughing besides the huff-coughs performed during ACT intervention period. Any additional coughs will not be controlled for, but will be recorded and evaluated as a covariate in data analyses.

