**Hypothesis 1:** *Device-assisted airway clearance therapy using OPEP, HFCWO-vest, and whole-body vibration causes a demonstrable increase in MCC and expectorated sputum volume when compared to cough alone.*

**Hypothesis 2:** *Airway signaling molecules, including NO and purine nucleotides (e.g. ATP, adenosine), are associated with the regulation of MCC and mediate the increase in mucus clearance that occurs following the application of mechanical stimuli from OPEP, HFCWO-vest, and whole-body vibration.*

We will test these hypotheses through these specific aims:

**Specific Aim 1:** Measure the effects of 4 different ACT modalities on MCC, using gamma scintigraphy.

**Specific Aim 2:** Measure the effects of different ACT modalities on proposed regulators of MCC, including nucleotide levels (via exhaled breath condensate collection) and exhaled NO.

**Specific Aim 3:** Examine associations between biomarkers of airway mechanical stimulation and measured MCC.

**Specific Aim 4:** Determine what study characteristics would be needed to more fully assess the effectiveness of ACTs, including sample size, study design features, and outcome measures.

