## Data analysis:

[name], biostatistician for the UNC CF Center, has been closely involved in the study design and will be responsible for overseeing the database creation and management, as well as performing final statistical computations during data analysis.

**Primary comparison:** MCC will be visualized using a whole right lung clearance vs. time plot from immediately after isotope inhalation through 274 minutes post-inhalation. The area under this curve (AUC-Clr274), will be used to reflect “total clearance”, and will serve as the primary outcome of this study. We will compare AUC-Clr274 in huff-cough alone to AUC-Clr274 measured with each of the ACT modalities (HFCWO-vest, OPEP device, and WBV device).

**Secondary comparisons:** AUC-Clr over other intervals (i.e. 94 min and 180 min), and from other lung regions of interest (i.e. peripheral and central lung zones) will be calculated and compared in similar fashion as above. Furthermore, the change in the rate of clearance (represented by the slope of the MCC curve,  $d\text{Clr}/dt$ ) before (0-16 minutes of MCC curve;  $d\text{Clr}/dt_{0-16}$ ) versus during/after the initial ACT intervention (16 – 56 minutes;  $d\text{Clr}/dt_{16-56}$ ) will be used to compare the immediate effects of each ACT versus. huff coughs alone. The mean changes in EBC purines concentrations and FeNO, (before vs. after ACT) will be calculated. If these are found to be different from zero, a comparison between huff-cough alone and each of the ACT modalities will be made. Total sputum weights and % solids at baseline and after each ACT 40 minute period will be compared across each of the ACT modalities. We will also assess for a relationship between changes in EBC measurements, FeNO, and changes in MCC.

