**Table 1**

	Baseline, mean (SD)	Post-HS, mean (SD)	Mean Change (SD)
AUC-Clr 180	17.4 (11.5)	30.5 (11.6)	13.1 (9.4)
AUC-Clr 360	47.4 (26.6)	89.9 (27.2)	42.4 (21.2)
Interpolated AUC-Clr 270	32.4 (19.0)	60.2 (19.1)	27.7 (15.1)

We predict that the observed mean change in AUC-Clr240 after an ACT will be somewhat smaller because this study uses a baseline that likely will be accelerated by a partially active intervention (huff cough). Therefore, we estimate a more conservative predicted effect size of 20.0 (72% of that observed after HS) with the same estimate of variability (SD 15.1) in our sample size calculations. Using these data, a dependent effect size index,  $d_z$  of 1.33 was calculated for the AUC-Clr240 variable. Using G\*Power (v3.1) and a paired, 2-tailed t-test to compare two means, we estimate that 7 subjects will be needed to detect a statistically significant difference ( $\alpha = 0.05$ ) (Figure 5). Given that we will be making multiple comparisons, wish to explore correlations between MCC and secondary outcomes, and to buffer against potential subject drop-out, we plan to enroll 10 subjects into this study.

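### Sputum is compared only as wet weight and percent solids; adding solids mass would show whether a heavier sample holds more mucus or only more fluid

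*Combined protocol and SAP*

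**What the plan says.** Hypothesis 1 (Section 1, Specific Aims) states that device-assisted clearance "causes a demonstrable increase in MCC and expectorated sputum volume when compared to cough alone". Under Sputum Collection and coughs, the material to be gathered is "All expectorated sputum from the start of the first ACT period through 274 minutes post isotope inhalation", and it "will be collected and weighed to assess total volume", so weight stands in for volume. The same paragraph gives the collection instruction, "Subjects will be encouraged to expectorate rather than swallow their sputum", and names the two measures: "This sputum will be analysed by total weight and percent solids".

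The Data analysis section lists the comparison among the secondary ones: "Total sputum weights and % solids at baseline and after each ACT 40 minute period will be compared across each of the ACT modalities". It then applies a repeated measures model, with subjects as random factors, to primary and secondary outcomes alike.

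No section derives the product of weight and percent solids. None describes separating saliva, rinsing the mouth or limiting evaporation before weighing. None says whether percent solids is measured on the whole collection, an aliquot or a selected plug.

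**The concern.** Wet weight is the sum of mucus and whatever fluid comes with it. Saliva raises wet weight and lowers percent solids together; so does extra airway water. With only these two measures, a device that made subjects spit more fluid could be reported as clearing more sputum, in apparent support of Hypothesis 1.

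Sputum is secondary here but not incidental. Section 4 (Rationale) gives effect size and variability for sputum volume as a purpose of the pilot. The Second Intervention Period is meant partly to find the best timing for sputum measurement. Specific Aim 4 is to inform the outcome measures of later trials. A measure that cannot tell mucus from fluid would carry that ambiguity forward.

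**Working it through.** **Inputs from the documents.** Outcomes: wet weight and percent solids. Collection runs from the first intervention (minute 16) to minute 274, i.e. 274 − 16 = 258 minutes. OPEP: 10 exhalations per segment × 6 segments × 2 sessions = 120 per visit.

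**Assumed inputs (the documents give none).** True sputum W = 5–10 g with solids fraction p = 5–7%; added saliva S = 2–10 g with solids fraction q = 0.5–1%. As a harder test, p down to 3%.

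**1. The plan's own figure.** The only sizing is for the clearance AUC. The standardised effect is 20.0/15.1 = 1.32 (the plan gives 1.33). An exact two-sided paired t-test at 5% has power 0.74 with 6 subjects, 0.83 with 7 and 0.96 with 10, so the stated 7 for 80% power is reproduced. There is no sizing for sputum, and nothing below changes N.

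**2. Mass balance.** With water loss L:
- wet weight = W + S − L
- percent solids = (Wp + Sq)/(W + S − L)
- product (solids mass) = Wp + Sq

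L cancels. With L = 0, saliva raises wet weight by S/W and solids mass by Sq/(Wp) = (q/p) × S/W. The ratio q/p runs from 0.5/7 = 7% to 1/5 = 20%. In the harder case (p 3%, q 1%) it is 1/3.

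**3. Range under the assumptions.**
- Wet weight: +20% (2/10) to +200% (10/5).
- Solids mass: +1.4% (2 × 0.005/(10 × 0.07)) to +40% (10 × 0.01/(5 × 0.05)).
- Percent solids starting at 5.0%: down to 4.3% (0.52/12) or 2.0% (0.30/15).
- 5 g sputum + 5 g saliva: wet weight +100%, solids mass +7% to +20%.

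**4. What each measure shows, starting from 5 g at 6% (0.30 g solids).**

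| Change | Wet weight | Percent solids | Solids mass |
|---|---|---|---|
| 2 g more sputum at 6% | +40% | 0% | +40% |
| 2 g saliva at 0.5–1% | +40% | −26% to −24% | +3% to +7% |
| 2 g airway water | +40% | −29% (0.30/7 = 4.29%) | 0% |
| 20% water loss | −20% | +25% | 0% |

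Wet weight is the same in the first three rows; solids mass separates the first from the next two. It does not separate saliva from airway water.

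**5. Can the planned pair be read jointly instead?** Only in part. If wet weight rises 40%, solids mass is unchanged when percent solids falls by 1 − 1/1.4 = 28.6%, higher if it falls less, and lower if it falls more. The direction of the two results does not settle it. Nor do group means, because the mean of a product is not the product of means; the value has to be formed per subject and collection.

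**6. Condition for the product to work.** If percent solids came from a saliva-free plug, the product would be (W + S)p and would rise by S/W, the full wet-weight bias: +100% in the 5 g + 5 g case.

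**7. Saliva that does not differ by modality.** One illustrative simulation used 10 subjects and paired t-tests on logs. It assumed median sputum 5 g, within-subject log SD 0.3, p fixed at 6%, saliva with median 2 g (log SD 0.8) at 0.75% solids, and water loss of 0–20%, all distributed alike at both visits. With no true effect, all three measures rejected about 5% of the time. With a true 1.5-fold rise in sputum, power was 0.41 for wet weight, 0.12 for percent solids and 0.75 for solids mass. Equal contamination therefore costs precision but does not create false positives. Fixing p, with no error in percent solids, favours solids mass, so the power gap is only indicative.

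**The case against.** The strongest objection is to making solids mass the sputum outcome in place of the planned ones. Hypothesis 1 names volume. The CF and MCC section traces mucostasis to dehydration, and the Biomarkers of Mucus Clearance section proposes that mechanical stimulation acts through ion transport. A device that truly hydrates mucus would raise wet weight and lower percent solids while leaving solids mass where it was. Solids mass is blind to that effect. This stands: the measure should be added, and the other two should not be demoted.

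Several stronger readings are tempting, and the documents do not support them.
- A reader might infer that the OPEP comparison is biased by saliva, since only that device adds 120 mouthpiece exhalations. But every visit, huff-cough included, has a FeNO manoeuvre and seven minutes of condensate breathing at minute 56, within the collection window. Nothing shows how much saliva reaches the collection under any modality, and the argument offers nothing for the vest or the plate.
- A reader might infer that evaporation distorts the comparison between modalities. The window and timetable are the same at all four visits and comparisons are within subject, so losses should be similar.
- A reader might infer that the product is free of saliva bias and already in hand. It retains up to 40% in the assumed range and, if percent solids is not representative of the weighed material, the whole bias.

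It is also fair to say that reporting weight and percent solids together makes dilution visible, and that if both are recorded on the same material the product can be computed later without loss of data. The first is only partly sufficient (step 5 of the working). The second is true, but it leaves a choice among sputum measures to be made after the results are seen.

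**Conclusion.** The point holds as an optional improvement. As planned, a rise in wet weight cannot be attributed to more expelled mucus rather than added fluid, and a derived variable from two values already planned would largely resolve that. The algebra needs two things: saliva must be more dilute than sputum, and percent solids must represent the weighed collection. Under the assumed fractions (p 5–7%, q 0.5–1%), solids mass carries 7–20% of the saliva shift in wet weight, and one third at p 3%, q 1%. The gram amounts behind the +20% to +200% range are assumptions throughout, so no actual bias is demonstrated. The plan does not contradict itself here, and the primary clearance AUC and the sample size are untouched.

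**What to change.** In Sputum Collection and coughs and in Data analysis:
- Prespecify total solids mass as an additional sputum outcome for Hypothesis 1: wet weight × percent solids, multiplied within each collection and then summed over the visit. Compare it within subject with huff-cough in the repeated measures model already planned.
- Keep wet weight and percent solids as planned outcomes, and interpret the three together. State that a rise in wet weight without a rise in solids mass will not be read as more mucus expelled.
- State that percent solids is measured on the whole, homogenised, weighed collection or on a representative aliquot of it.

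The cost is one derived variable, a few lines of wording and one more secondary outcome among several. If current practice is to measure a selected plug, sample handling would also have to change. Solids mass will not detect hydration, will not separate saliva from airway water, and will not recover swallowed sputum.

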#### **5. Experimental Design and Methods:**

**Key inclusion criteria:** Adults with confirmed diagnosis of cystic fibrosis aged 18 years and older.

**Key exclusion criteria:** Pregnant or lactating women, individuals with severe lung disease (FEV1 <30%), or with exacerbations of lung disease requiring antibiotics or medication change within four weeks prior to enrolment. Individuals unable to use vest-based HFCWO, oscillatory PEP device, or who require oxygen supplementation at rest. We will also exclude individuals with significant balance or gait impairment preventing the individual from tolerating being positioned on a vibrating platform.

**Study design:** Ten (10) adult CF subjects will be recruited from the CF clinic at UNC, and will have a screening visit and four subsequent study visits. At Study Visit 1 huff-cough alone (control) will be performed while the order of the 3 remaining airway clearance therapy (ACT) treatments received at Study Visits 3-5 will be randomized: oscillatory PEP (positive expiratory pressure), high frequency chest wall oscillatory vest, and the vibrating plate device. Only one ACT device will be used at any given visit as adjuncts to huff-coughing, with the same cough regimen used at all study visits (Figures 3 & 4). Study visits will be at least three and no more than 21 days apart. Subjects who are prescribed hypertonic saline, dornase alfa, long-acting bronchodilators, and/or airway clearance will be asked to withhold use of these agents/activities after midnight before each study visit after screening. No bronchodilators will be used as part of this study.

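### The plan leaves open whether device comparisons adjust for unscheduled coughs; adjusting for coughs after minute 16 would no longer estimate the total effect in Hypothesis 1

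*Combined protocol and SAP*

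**What the plan says.** The sentence at issue closes the section Sputum Collection and coughs: "Any additional coughs will not be controlled for, but will be recorded and evaluated as a covariate in data analyses". The same section tells subjects "to cough only when naturally compelled to do so", and adds that during imaging "subjects will be asked to minimize additional coughing besides the huff-coughs performed during ACT intervention period".

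Scheduled coughing is fixed by design, "with the same cough regimen used at all study visits" (section 5, Study design). Between visits, therefore, only the unscheduled coughs are free to differ.

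On timing, the Mucociliary Clearance section states that "images will be obtained for 16 minutes prior to any intervention". The first ACT then starts at minute 16. A second session begins at minute 180, with its ACT at minute 196.

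Hypothesis 1 is that device-assisted therapy "causes a demonstrable increase in MCC and expectorated sputum volume when compared to cough alone". The primary outcome is the area under the right-lung clearance curve to 274 minutes, which "will be used to reflect “total clearance”, and will serve as the primary outcome of this study". The Data analysis section compares it with a repeated measures model that has a random subject effect, and it lists no covariate.

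**The concern.** A cough that follows the ACT is a post-treatment variable. If a device moves mucus to where it triggers cough, the extra coughs are part of how the device works, and they add to clearance and sputum. Hypothesis 1 and the primary outcome both concern the whole effect of adding a device to huff-cough. Once the later cough count is in the model, the device coefficient describes at most the part of the effect that does not run through extra coughing. It is also exposed to anything that drives both coughing and clearance at that visit, such as mucus burden.

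The plan does not say whether the covariate belongs to the primary model, a secondary model or a supportive one. It does not say which minutes are counted, or which result governs if adjusted and unadjusted answers differ. With 10 subjects and three device comparisons, that choice could be made after the data are seen.

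**Working it through.** **1. The plan's own figure.** Inputs from the Sample size estimate: change 20.0, SD of change 15.1, paired two-sided t-test, α = 0.05, 7 subjects needed, 10 to be enrolled. The target power of 80% is under Missing Data/Subject Drop Out.

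- Standardised effect: d = 20.0 / 15.1 = 1.325 (plan: 1.33).
- Power = P(T > t₀.₉₇₅,ₙ₋₁) + P(T < −t₀.₉₇₅,ₙ₋₁), where T is noncentral t with n − 1 degrees of freedom and noncentrality d√n.
- n = 6 gives 0.737 and n = 7 gives 0.830, so 7 is reproduced. n = 10 gives 0.960.

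**2. How much of the count precedes the ACT.** Minutes 0–16 are 16 of the 274 minutes in the primary outcome: 16/274 = 5.8%. Imaging itself runs over 0–94 and 180–274, which is 94 + 94 = 188 minutes, and 16/188 = 8.5%. The imaging in minutes 180–196 precedes the second ACT but follows the first, so it does not count as pre-treatment.

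**3. What adjustment estimates.** Let E be the total device effect, δ the change in unscheduled coughs that the device causes, and b the AUC gained per cough. If nothing unmeasured drives both coughing and clearance:

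- unadjusted device coefficient = E
- adjusted device coefficient = E − bδ

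The documents give neither δ nor b. Take E = 20 and, as an assumption, b = 2. A simulation of 10 subjects × 4 visits (fixed subject effects, 3,000 runs per row, SD of the paired difference set to 15.1 in the first five rows) agrees with the formula:

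| Assumed δ | E − bδ | Simulated unadjusted | Simulated adjusted |
|---|---|---|---|
| 0 | 20 | 19.8 | 19.9 |
| +2 | 16 | 20.0 | 15.9 |
| +4 | 12 | 20.0 | 11.9 |
| +5 | 10 | 20.0 | 10.0 |
| −2 | 24 | 20.0 | 24.0 |
| +4, plus an unmeasured factor that raises coughs and lowers clearance | 12 | 19.9 | 17.8 |

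In the last row the adjusted figure is neither the total effect (20) nor the effect not acting through cough (12).

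**4. Illustration on the plan's power scale.** Let m = bδ/E be the share of the effect acting through coughs. The adjusted effect is 20(1 − m). SD is held at 15.1, n = 10, with the formula from step 1:

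| Assumed m | Adjusted effect | d | Power |
|---|---|---|---|
| −25% | 25.0 | 1.656 | 0.996 |
| 0 | 20.0 | 1.325 | 0.960 |
| 10% | 18.0 | 1.192 | 0.917 |
| 25% | 15.0 | 0.993 | 0.798 |
| 50% | 10.0 | 0.662 | 0.464 |

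Holding the SD fixed is a simplification, because a covariate changes both the residual variance and the standard error of the device term. The simulation includes both. At δ = +5 (m = 2 × 5/20 = 50%) its adjusted model detected the device in 31% of runs, against 98% unadjusted.

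**The case against.** The best reply is that the plan never says the primary comparison will be adjusted. The sentence only promises to evaluate coughs as a covariate, and the model in the Data analysis section has none. Read at face value, the primary comparison is already unadjusted. This stands: a reader might infer that the plan specifies an analysis that strips out device benefit, and the documents do not support that.

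Two other inferences also go too far.

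- *All unscheduled coughs follow the ACT.* Those in minutes 0–16 do not. They cannot result from that visit's device and may be adjusted for without this problem.
- *Adjustment must bias devices toward zero, or would reorder them.* The direction depends on whether a device raises or lowers coughing, and no data are given. With no device effect on coughing there is no bias. With less coughing the device effect is inflated. Nothing calculated here shows a change in ranking.

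It is also fair to say that the fixed cough regimen and the request to minimise coughing during imaging should narrow this pathway. A cough-adjusted model has a legitimate use as well: clearance not due to extra coughing is relevant to the signalling mechanism in Hypothesis 2, and this is a pilot. Both points limit the size of the problem. Neither says which analysis answers Hypothesis 1, and coughing when compelled is still allowed.

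**Conclusion.** The concern holds as an undefined analysis instruction that could change the quantity estimated. If coughs from minute 16 onward enter a device-versus-huff-cough model, the coefficient is not the total effect in Hypothesis 1 whenever the device alters coughing and coughing is related to clearance. That conclusion follows from the timing and the hypothesis and needs no numerical assumption.

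The size is not known. The drop in power from 96% to 92%, 80% or 46% rests on assumed shares of 10%, 25% and 50% and a fixed SD. A share of zero leaves 96%, and a negative share raises it. These figures illustrate sensitivity; they are not a forecast, and they do not describe the unadjusted model in the Data analysis section. The planned sample size is unaffected. The point should be settled before the data are analysed.

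**What to change.** Replace the last sentence of Sputum Collection and coughs with:

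> Additional coughs during all MCC imaging are recorded separately for minutes 0–16 (pre-ACT) and from minute 16 onward. Post-ACT coughs are compared between modalities as an outcome and are not a covariate in the primary or secondary device-versus-huff-cough models. Any model adjusted for post-ACT coughs is exploratory and is described as the effect not acting through additional cough; pre-ACT coughs (minutes 0–16) may be adjusted for as a sensitivity analysis.

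At the huff-cough visit the same split at minute 16 applies, since the huff-cough period starts there.

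The cost is this wording and a split of a tally that is already planned. No counting is needed in the break between sessions, and no subjects are added. The one statistical price is that the unadjusted comparison keeps some random variation due to coughing.
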